The duration of treatment with fitusiran is 9 months. The estimated total time on study, inclusive of screening, for each patient is up to 11 months for all patients who enroll in the extension study and patients in the on-demand arm who do not enroll in the extension study. The estimated total time on study may be up to 17 months in fitusiran treatment arm patients who do not enroll in the extension study due to the requirement for an additional 6 months of follow-up for monitoring of AT levels.

Statistical Methods*Sample Size Calculation*

Assuming a mean ABR of 18 with standard deviation (SD) = 14 in the on-demand arm (patients randomized to receive only factor concentrates) and a mean ABR of no more than 4 with SD = 6 in the fitusiran treatment arm (patients randomized to receive fitusiran) in either the efficacy period or treatment period, with a sample size of 32 evaluable patients in the on-demand arm and approximately 64 evaluable patients in the fitusiran treatment arm, it is projected that the study will have greater than 90% power for detecting treatment difference in mean ABRs. This power estimation was based on a negative binomial regression model with a 2-sided type I error rate of 0.05.

The planned sample size is 120 randomized patients assuming a 20% drop-out rate.

Analyses

The primary analysis will be performed on the intent-to-treat (ITT) analysis set which includes all randomized patients. The primary endpoint will be based on the bleeding episodes occurring in the efficacy period (Day 29 to Day 246) including the data collected after discontinuation of investigational medicinal product (IMP). To avoid confounding the treatment effect, bleeding data during and after major surgery, antithrombin (AT) administration, major trauma, or after initiation of prophylaxis treatment with factor concentrates will be excluded from the primary analysis.

The number of bleeding episodes will be analyzed using a negative binomial model with fixed effects of treatment arm, the number of bleeding episodes in the 6 months prior to study entry (≤ 10 vs >10), and hemophilia type (hemophilia A or B). The logarithm number of days that each patient spends in the efficacy period matching the bleeding episode data being analyzed will be included as an offset

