8. STATISTICS

A Statistical Analysis Plan (SAP) will be finalized before database lock. The plan will detail the implementation of the statistical analyses in accordance with the principal features stated in the protocol.

The primary efficacy and safety analyses will be performed after all patients have either finished the 9-month treatment period or discontinued from the study.

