8.2.5.1. Primary Endpoint

The primary analysis will be performed on the ITT Analysis Set and will include all bleeding episodes occurring in the efficacy period (Day 29 to Day 246) including bleeding episode data collected after discontinuation of IMP. If a patient does not have bleeding episode data collected after Day 28 (eg, due to early study discontinuation), the available bleeding episode data starting from Day 1 will be used as bleeding episode data of the fitusiran period in the primary analysis. To avoid confounding the treatment effect, bleeding episode data during and after major surgery, AT administration, major trauma, or initiation of prophylaxis treatment with factor concentrates will be excluded from the primary analysis.

The number of bleeding episodes will be analyzed using a negative binomial model with fixed effects of treatment arm and the number of bleeding episodes in the 6 months prior to study entry (≤ 10 vs > 10) and hemophilia type (hemophilia A or B). The logarithm number of days that each patient spends in the efficacy period matching the bleeding episode data being analyzed will be included as an offset variable to account for unequal follow-up time due to early withdrawal or surgery. The p-value comparing bleeding rates in the 2 treatment arms and the ratio of bleeding rates in the fitusiran treatment arm to the on-demand arm along with its 95% CI will be presented. The estimated mean ABRs in each of the 2 treatment arms along with their 95% CIs will be presented from this model. In addition, summary statistics for ABR, including median and interquartile range, will be presented for each treatment arm, where ABR is defined as:

$$\frac{\text{total number of qualifying bleeding episodes}}{\text{total number of days in the respective period}} \times 365.25$$

Patients who discontinue treatment during the study will be encouraged to continue recording bleeding episode data.

Sensitivity analyses will be performed to evaluate the impact of missing data under different missing data mechanisms and details will be specified in the statistical analysis plan.

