In the ATLAS-A/B study (ALN-AT3SC-004 [EFC14769]), fitusiran is evaluated as prophylaxis to prevent or reduce the frequency of bleeding episodes in patients with hemophilia A or B without inhibitory antibodies to FVIII or FIX and who are being treated with on-demand factor concentrates. This statistical analysis plan (SAP) contains definitions of analysis populations and endpoints, outlines the timing of statistical analyses, and provides a comprehensive description of statistical analyses to be implemented to assess the clinical efficacy and safety of Study ALN-AT3SC-004 (EFC14769), original protocol amendment 1 (referred to as Global Protocol hereafter) dated 16 November 2016 and original protocol - United States amendment 1 (referred to as US Protocol hereafter), dated 09 November 2017, and protocol amendment 2 dated 27 June 2018. The contents of this SAP will apply to both versions of protocols amendment 1 and amendment 2 unless otherwise specified, where the methodologies for the two versions of protocol amendment 1 and amendment 2 are discussed separately. The data analyses will be used for the Clinical Study Report.

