2.5 Modifications to the statistical section of the protocol

This section summarizes major changes to the protocol statistical section. These changes are made before the first patient is randomized. The statistical analysis plan history table below gives the timing, rationale, and key details for major changes to the protocol statistical section.

The first patient was enrolled on March 1, 2018. There are no planned interim analyses.

Protocol Amendment statistical changes

Amendment number	Date approved	Rationale	Description of statistical changes
1	16-Nov-2017	Revised the definition of efficacy period based on on-treatment strategy for the primary analysis of primary endpoint in assessing the primary objective of the study (ICH E9 (R1)).	Efficacy period (Day 29 to Day 246) defined in the protocol is changed to (Day 29, earliest of (Day 246, or the last day of bleeding follow up) excluding the period for each intercurrent event.
1	16-Nov-2017	Added exclusion periods due to fitusiran treatment discontinuation, major or minor surgery, prophylactic treatment with emicizumab or factor since including bleeding events in these periods in the primary analysis would bias fitusiran treatment effect.	Exclusion period for each intercurrent event is described in details in Section 6.3

[figure not shown]
[figure not shown]

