Onset Period	Day 1 to the earlier of Day 28 and the last day of bleeding follow up
Efficacy Period	Day 29 to the earliest of (Day 246, or the last day of bleeding follow up)

Treatment Period	Onset period plus the efficacy period
------------------	---------------------------------------

The last day of bleeding follow up is defined as the deactivation date captured in eDiary.

If a patient does not have bleeding episode data collected after Day 28 due to early study discontinuation, the efficacy period will be from Day 1 to the earlier of date of study discontinuation and the last day of bleeding follow up.

The onset period, efficacy period and treatment period also exclude the period of following intercurrent events to avoid confounding of treatment effect for the primary efficacy analysis based on On-Treatment Strategy.

- After one month (28 days) from fitusiran treatment discontinuation in the fitusiran efficacy period. Excluding bleeding data after one month from fitusiran treatment discontinuation is considered reasonable and adequate considering that fitusiran is dosed monthly and EOS is one month after last dose of fitusiran.
- Perioperative period of major surgery. The perioperative period is defined as the day of the surgery through the final day on which supplemental hemostatic or antithrombotic treatments are administered as part of the perioperative treatment plan.
- Period of minor surgery is defined as the Perioperative period of surgery above or to 72 hours from the end of surgery, whichever is later.
- Period of Antithrombin treatment is defined as the first day of antithrombin treatment through the final day on which antithrombin or other anticoagulant therapies are administered plus 5 half-lives of that specific product.
- After prophylactic treatment with emicizumab, BPA or factor.

The summary statistics for number of patients who are lost-to-follow-up and who had each intercurrent event will be provided.

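### Protocol amendment 2 and the SAP set different exclusions for the primary analysis, no planned analysis uses the protocol's set, and the Day 1 fallback misses followed patients with no evaluable efficacy days

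*SAP*

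**What the plan says.** Protocol 8.2.5.1 says the primary analysis "will include all bleeding episodes occurring in the efficacy period (Day 29 to Day 246) including bleeding episode data collected after discontinuation of IMP". It adds that "bleeding episode data during and after major surgery, AT administration, major trauma, or initiation of prophylaxis treatment with factor concentrates will be excluded". The synopsis repeats both rules. Of the SAP, Protocol section 8 says: "The plan will detail the implementation of the statistical analyses in accordance with the principal features stated in the protocol".

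SAP 6.3 defines the periods for an on-treatment primary analysis and removes, among others, the time "After one month (28 days) from fitusiran treatment discontinuation in the fitusiran efficacy period". Side by side:

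| Event | Protocol 8.2.5.1 | SAP 6.3 |
|---|---|---|
| Fitusiran stopped | Later data kept to Day 246 | Dropped beyond 28 days |
| Major surgery | Dropped from then on | Perioperative period only |
| Minor surgery | Not excluded | Perioperative period or 72 hours, whichever ends later |
| Antithrombin | Dropped from then on | Treatment plus 5 half-lives |
| Major trauma | Dropped from then on | No exclusion |
| Prophylaxis | Factor, from its start | Factor, BPA or emicizumab, no end given |

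SAP 2.5 logs the change against amendment 1: "Added exclusion periods due to fitusiran treatment discontinuation, major or minor surgery, prophylactic treatment with emicizumab or factor". It also states: "The first patient was enrolled on March 1, 2018". The SAP introduction says the SAP covers "protocol amendment 2 dated 27 June 2018".

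The treatment-policy analysis (SAP 6.3.1.2) keeps bleeds after discontinuation and removes surgery-related events only. A variant removes nothing.

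The Day 1 fallback (SAP 6.3, 6.3.1.1 and 6.3.1.3) starts a patient's efficacy period at Day 1 when no bleeding data were collected after Day 28. Two of the three places tie this to early study discontinuation; 6.3.1.1 gives that only as an example. The model's offset is the log of evaluable duration.

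**The concern.** Whether bleeds after stopping drug count towards the primary endpoint is a principal feature, and the two current documents disagree on it. Amendment 2 is later than the logged change and later than first enrolment. Its change table lists an edit to section 8.2.5.1, yet the protocol's rule stayed. SAP 2.5 explains the on-treatment choice, but not the lost trauma exclusion or the time limits on the surgery and antithrombin exclusions. The trial is open-label, and if bleeding rises off drug, the SAP rule favours fitusiran.

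The fallback is a second problem. It depends on whether data were collected after Day 28, not on whether any evaluable days remain. A followed patient in either arm who starts prophylaxis by Day 28 has data but no days. He leaves the Global primary, the US second endpoint, and endpoints 3 and 4 in both hierarchies. In the time-to-first-bleed analysis he would be censored before the Day 29 origin. The planned counts of intercurrent events and the missing-data summary do not identify him.

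How often this happens depends on a trigger that SAP 6.3 leaves undefined. The eDiary (Protocol 7.2.1) separates prophylaxis from doses taken ahead of activity, while the per-protocol criteria in SAP 4 count such doses as prophylaxis. SAP 6.3 does not say whether one dose starts an open-ended exclusion.

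**Working it through.** **Plan's own figures.** Inputs (SAP 5.1): ABR 18 (SD 14) in 32 on-demand patients, 4 (SD 6) in 64 fitusiran patients, 20% drop-out.
- N = 96/(1 - 0.20) = 120, as stated.
- Window Day 29 to 246 = 218 days, t = 218/365.25 = 0.597 years. Dispersion k = (SD² - μ/t)/μ² = 0.51 on-demand, 1.83 fitusiran.
- SE of the log ratio = √[(1/(18t) + 0.51)/32 + (1/(4t) + 1.83)/64] = 0.2325. Then |ln(4/18)|/0.2325 = 6.47, and power exceeds 99.99%. This agrees with the stated figure of over 90%.

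**(a) Keeping or dropping bleeds after discontinuation.** Assumed: 10% or 20% of fitusiran patients stop and stay in follow-up; last dose equally likely on Day 1, 29, ..., 197; off-drug ABR r.
- With the cut at last dose + 28 days, the efficacy days lost are 217, 189, ..., 21. Their mean is 119, and 119/218 = 0.546.
- Off-drug share of arm time: f = 0.0546 (10% stop) or 0.1092 (20% stop).
- SAP rule: 4/18 = 0.222. Bleeds kept: (4(1 - f) + r·f)/18.

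| r | 10% stop | 20% stop |
|---|---|---|
| 4 | 0.222 | 0.222 |
| 11 | 0.243 | 0.265 |
| 18 | 0.265 | 0.307 |

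Simulated negative binomial fits at r = 18 gave medians of 0.262 and 0.297, with power 99.8% and 99.0%. Timing matters: if all 20% took their last dose on Day 57, the closed form gives 0.337.

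**(b) What the treatment-policy analysis leaves uncovered (prophylaxis only).** Assumed: a share q of the on-demand arm starts factor prophylaxis uniformly over the window, so g = q/2 of that arm's time; ABR on prophylaxis p.
- Treatment policy = 4/(18(1 - g) + p·g). For p from 2 to 6: 0.227 to 0.226 (q = 5%) and 0.233 to 0.230 (q = 10%). The protocol rule gives 0.222.
- Adding stoppers, half of them on prophylaxis from the cut: treatment policy = (4(1 - f) + r·f/2 + p·f/2)/(18(1 - g) + p·g); protocol rule = (4(1 - f) + r·f/2)/(18(1 - f/2)).
- Lowest difference (20% stop, r = 18, p = 2, q = 0): 0.2586 - 0.2671 = -0.0085. Highest (20% stop, r = 4, p = 6, q = 10%): 0.2362 - 0.2222 = +0.0139.

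**(c) Zero-day patients.** For a patient followed to Day 246, prophylaxis starting by Day 28 leaves 0 evaluable days, and starting on Day 29 leaves 0 or 1. A single fitusiran dose on Day 1 leaves 0 or 1, depending on how the 28 days are counted. At 0 days the offset is log(0).

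Suppose these patients bleed at twice their arm's mean. Dropping m of 40 on-demand patients multiplies the ratio by 1 + m/40; dropping m of 80 fitusiran patients divides it by 1 + m/80. The simulation used 500 trials per scenario, 80 vs 40 patients, the dispersions above, no strata, prophylaxis starting uniformly on Day 2 to 28, and onset bleeding at the patient's own rate.

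| Dropped | By hand | Simulated | With fallback |
|---|---|---|---|
| 1 of 40 on-demand | 1.025 | 1.027 | 1.016 |
| 2 of 40 on-demand | 1.050 | 1.047 | 1.027 |
| 4 of 40 on-demand | 1.100 | 1.097 | 1.047 |
| 2 of 80 fitusiran | 0.976 | 0.976 | 0.981 |
| 4 of 80 fitusiran | 0.952 | 0.956 | 0.965 |

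If they bleed at the arm mean, every simulated value lies between 0.997 and 1.000.

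**Subgroups.** About 26 hemophilia B patients gives 26/3 = 8.7 on-demand, so one patient is 1/8.7 = 11.5%. About 10 adolescents gives 3.3 on-demand; losing one of 3 leaves 2, below the three-per-arm rule in SAP 6.3.1.4.

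**The case against.** Protocol 8.2 calls its methods summaries and leaves fuller plans to the SAP. SAP 2.5 gives a rationale, says the changes preceded first randomization, and refers to 6.3 for details; 6.3.1.1 and 6.3.1.2 name the on-treatment estimand as primary. So the change is disclosed. That stands, but it does not remove the conflict: amendment 2 still carries the other rule, and the trauma, surgery and antithrombin differences go unexplained.

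The large shift in (a) would already appear in the treatment-policy analysis. The gap in (b) is small beside a 95% interval of roughly 0.14 to 0.35 (0.222 × exp(±1.96 × 0.2325)), and in the prophylaxis-only case treatment policy is less favourable to fitusiran than the protocol rule. Both points stand. Trauma, surgery and antithrombin differences were not quantified.

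Zero-day patients should be few. Entry requires on-demand treatment, and Protocol 6.3.1.2 tells fitusiran patients not to use prophylaxis. They stay in the treatment-policy model, and in treatment-period ABR if prophylaxis starts after Day 1. The protocol's own fallback has the same gap, so this part is not a conflict between documents. On-demand losses of heavier bleeders count against fitusiran.

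The fallback also brings onset days, before the full drug effect, into an efficacy-period estimate, and it removes only about a fifth to a half of the simulated shift. The adolescent subgroup is fragile anyway: with 10 patients at 2:1, the binomial chance of fewer than 3 on-demand is about 30%. The synopsis definition of on-demand use supports reading prophylaxis as a regular regimen, although Protocol 6.3.1.2 and SAP 4 point the other way.

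**Conclusion.** The concern holds and should be fixed. The exclusion rules differ on every event in the table, and no SAP analysis reproduces the protocol's set. A stated rule also removes some randomized patients from a model described as ITT, which is more than missing detail. The undefined 28-day anchor and single-dose trigger would, taken alone, only need clarifying.

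The effect is on the estimate, not on significance. The choice of rule could turn a 78% reduction into 69% to 78% under (a). The top of that range is an extreme case: 20% stopping, with full loss of effect right after the cut, whereas SAP 6.3.1.2 describes gradual loss. The part no planned analysis would show is about 0.01 on the ratio in the scenarios of (b). Zero-day losses matter only if those patients bleed differently from their arm. Stopping, prophylaxis and off-drug bleeding rates are all assumptions; the plan's 20% is drop-out, which is a different quantity.

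**What to change.** 1. Reconcile protocol and SAP on the primary exclusion rules. If on-treatment stays primary, add one named sensitivity analysis using the inclusion and exclusion rules of Protocol 8.2.5.1, and explain in SAP 2.5 the dropped trauma exclusion and the bounded surgery and antithrombin periods.
2. Use one fallback wording in SAP 6.3, 6.3.1.1 and 6.3.1.3. It should cover any ITT patient with zero evaluable efficacy days for whatever reason, using Day 1 to the day before the first excluded period. Report by arm how many need it and how many still have zero days, for example with prophylaxis from Day 1. State whether a single preventive dose starts the prophylaxis exclusion. Apply the same fallback in the added analysis, labelled as an extension of the protocol rule.
3. State that the 28 days run from the last dose date, as the Covid-19 analysis in SAP 6.3.1.2 already does.

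The cost is SAP wording, a protocol alignment if that text is the one changed, and one more model run on data already collected. A slightly less favourable ratio may appear beside the primary result. The wider fallback mixes onset days into the efficacy-period estimate, as the SAP already accepts for early withdrawals.

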6.6. Elective and/or Emergency Surgery

If an urgent need for surgery arises during the study period, the study Medical Monitor will be informed and the perioperative hemostatic treatment plan will be communicated to the study Medical Monitor unless clinical circumstances do not allow.

It is recommended that, when possible, any elective non-dental major surgery be performed at a clinical study center.

For reference, see Appendix (Section 11.2.1) for definitions of minor and major surgery.

Perioperative Treatment Plan

In patients in both the on-demand arm and the fitusiran treatment arm undergoing surgery, a written perioperative treatment plan will be reviewed with the study Medical Monitor before conducting the procedure, unless clinical circumstances do not allow. In patients on fitusiran, the perioperative treatment plan should be developed using the same principles as bleed management described in Section 6.3.1 and the guideline below:

- If the clinical circumstance is such that the recommended doses and/or dose intervals in Table 4 are deemed insufficient for hemostasis, consider AT replacement and manage thrombotic risk as per Investigator practice for a hemophilia patient undergoing that particular surgery.
- Non-pharmacologic methods of thromboprophylaxis should also be employed as clinically indicated.

Fitusiran Treatment During the Perioperative Evaluation Period

For reference, see Appendix (Section 11.2.1) for definitions of minor and major surgery.

If the need for a major surgery arises during the trial and the procedure is not an emergency or urgent, it is recommended that the procedure be postponed until after completion of the trial.

For minor operative procedures, dosing with fitusiran may continue uninterrupted.

If the need for emergency or urgent major surgery arises during the trial, the patient should be managed medically according to the guidelines above. If a fitusiran dose is scheduled to occur on or in close proximity to the day of surgery, or anytime during the perioperative period, the dose should be withheld. The Perioperative Period is defined as the day of the surgery through

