the final day on which supplemental hemostatic or antithrombotic treatments are administered as part of the perioperative treatment plan. Fitusiran dosing may be resumed at the next scheduled visit following the Perioperative Evaluation Period at the discretion of the Investigator. If multiple consecutive doses of fitusiran are withheld, the Investigator will consult with the study Medical Monitor, who will determine if the patient may continue on study.

Perioperative assessments will be performed in patients undergoing surgery during the study as described in Appendix (Section 11.2.2) and as scheduled in Table 10.

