11.2. Perioperative Schedule of Assessments

11.2.1. Definitions of Minor and Major Surgery

Minor surgery is defined as any invasive operative procedure in which only skin, mucous membranes, or superficial connective tissue is manipulated and does not meet the criteria for major surgery (eg, dental extraction of <3 non-molar teeth). Minor surgical procedures may be performed at a local health care provider institution.

Major surgery is defined as any invasive operative procedure that requires any of the following:

- Opening into a major body cavity (eg, abdomen, thorax, skull)
- Operation on a joint
- Removal of an organ
- Dental extraction of any molar teeth or ≥ 3 non-molar teeth
- Operative alteration of normal anatomy
- Crossing of a mesenchymal barrier (eg, pleura, peritoneum, dura)

It is recommended that any elective non-dental major surgery be performed at a clinical study center, when possible.

11.2.2. Perioperative Assessments of Safety and Hemostatic Efficacy in Patients Undergoing Operative Procedures

In patients undergoing operative procedures during the treatment period, safety and hemostatic efficacy assessments will be performed according to the Perioperative Schedule of Assessments (described below and outlined in [Table 10](#)), where possible.

After a review of medical and surgery history has been completed, patients will have the following assessed as specified in the Perioperative Schedule of Assessments ([Table 10](#)): directed physical examination and assessment of vital sign measurements; clinical laboratory assessments including hematology (complete blood count, white blood count, red blood cell count, hemoglobin, hematocrit, platelets); coagulation (APTT, PT/INR, fibrinogen, D-dimer); hepatic assessments; and hemostatic efficacy assessments (rating scale based on ISTH Scientific and Standardization Committee [SSC] definitions).[\[10\]](#)

Table 10: Perioperative Schedule of Assessments in Patients Undergoing Operative Procedures

| | Perioperative Evaluation Period ^a | | | | |
|--|--|---------------------------------|-----------------------|---------------------------|-----------------------|
| | Preoperative Screening | Dental/Surgical Procedure Visit | Postoperative Visit 1 | Postoperative Visit 2 | Postoperative Visit 3 |
| | SDay -3 to SDay -1 | SDay 0 | SDay 1 ^b | SDay 2 to 14 ^c | SDay 28 ^d |
| Directed Physical Examination ^d | X | | | | X |
| Vital Sign Measurements ^e | X | | | | X |

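### SAP 6.3 gives minor surgery a 72-hour minimum exclusion and major surgery none, so a treated surgical bleed soon after a briefly covered major procedure could count in the primary ABR

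*SAP*

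**What the plan says.** SAP 6.3 (Efficacy Period and Treatment Period) lists the intercurrent events whose periods are taken out of the onset, efficacy and treatment periods for the primary, on-treatment analysis. Two of the items concern surgery.

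- Major surgery, with this window: "The perioperative period is defined as the day of the surgery through the final day on which supplemental hemostatic or antithrombotic treatments are administered" under the perioperative treatment plan. No minimum length is given.
- Minor surgery: "the Perioperative period of surgery above or to 72 hours from the end of surgery, whichever is later".

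The major-surgery wording follows the protocol's own definition of the perioperative period in Protocol 6.6, which ends on "the final day on which supplemental hemostatic or antithrombotic treatments are administered as part of the perioperative treatment plan". That definition also has no minimum.

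Protocol 8.2.5.1 states the exclusion for the primary analysis more broadly. It leaves out "bleeding episode data during and after major surgery, AT administration, major trauma" and data after factor prophylaxis is started, and sets no end point for the period after surgery.

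SAP 2.5 records the change of approach as "Added exclusion periods due to fitusiran treatment discontinuation, major or minor surgery, prophylactic treatment with emicizumab or factor" and refers to Section 6.3 for detail. It does not say why the major-surgery window is now tied to days of cover, or why only minor surgery has a time minimum.

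Protocol 11.2.1 classes a procedure as major on any of several criteria. These include an operation on a joint and "Dental extraction of any molar teeth".

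**The concern.** The exclusion exists to keep bleeding caused by surgery out of the comparison; SAP 6.3.1.1 says that including bleeds from such periods could bias the estimated effect. The minor-surgery rule accepts that surgical bleeding can outlast the last dose of cover. The major-surgery rule makes no such allowance, so the larger procedure can receive the shorter exclusion.

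A bleed that falls in the gap would enter the primary ABR as breakthrough bleeding. After joint surgery it could also enter the annualized joint bleeding rate, which is in the testing hierarchy of SAP 5.7. The SAP handles a residual surgical effect differently elsewhere: for the joint health score (SAP 6.3.3.6), data on an operated joint are excluded until 7 days after the perioperative period.

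**Working it through.** **1. The plan's own figures.** SAP 5.1 assumes a mean ABR of 18 (SD 14) on demand and 4 (SD 6) on fitusiran, with 32 and 64 evaluable patients, two-sided alpha 0.05 and 20% drop-out.

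- Randomized number: (32 + 64)/(1 − 0.20) = 120, that is 40 + 80. This matches the plan.
- Efficacy period: 246 − 29 + 1 = 218 days, or 218/365.25 = 0.597 years.
- Expected bleeds per patient: 18 × 0.597 = 10.74 on demand; 4 × 0.597 = 2.39 on fitusiran.
- Negative binomial dispersion, k = (variance − mean)/mean², from the stated SDs scaled to the period: 0.51 on demand, 1.83 on fitusiran.
- SE² of the log rate ratio = (1/10.74 + 0.51)/32 + (1/2.39 + 1.83)/64, so SE = 0.2325.
- log(4/18) = −1.504, giving power above 99.9%. With a common k of 1.83 it is 99.8%. Both are consistent with the stated figure of more than 90%.

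**2. The two windows applied to one case.** This case is an assumption; the documents do not describe it. Cover is given on the day of surgery only, one treated bleed starts on post-operative day 2, and the patient has no other bleeds.

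| | Major-surgery rule as written | With a 72-hour minimum |
|---|---|---|
| Days excluded | 1 | 4 (day of surgery plus 3) |
| Days analysed | 218 − 1 = 217 | 218 − 4 = 214 |
| Bleeds counted | 1 | 0 |
| Patient ABR | 1/217 × 365.25 = 1.68 | 0 |

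Under the minor-surgery rule the same bleed would already be excluded.

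**3. Size per bleed.** Over the full period, one counted bleed adds 365.25/218 = 1.68 to a patient's ABR. Across an 80-patient arm the mean moves by 1.68/80 = 0.02.

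**4. Size at trial level.** The documents give no count of such bleeds, so 1 to 5 is an assumed range. Follow-up among evaluable patients is 64 × 0.597 = 38.2 years on fitusiran and 32 × 0.597 = 19.1 years on demand.

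| Extra counted bleeds | Fitusiran mean ABR | On-demand mean ABR | Rate ratio |
|---|---|---|---|
| None | 4.00 | 18.00 | 0.222 |
| 1, fitusiran arm | 4.03 | 18.00 | 0.224 |
| 5, fitusiran arm | 4.13 | 18.00 | 0.230 |
| 1, on-demand arm | 4.00 | 18.05 | 0.222 |
| 5, on-demand arm | 4.00 | 18.26 | 0.219 |

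Power stays above 99.9% in every row.

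**The case against.** **Whether such a bleed would count.** Only treated bleeds enter the primary analysis (SAP 6.3), so a bleed that could count has been dosed. If those doses are recorded as part of the perioperative plan, the window extends and the bleed drops out. The SAP does not settle this, so the consequence is conditional. Two other rules can also remove the bleed: the separate antithrombin exclusion, if antithrombin was given, and the 72-hour merging rule, if an earlier bleed at the same site was treated. The merging rule does not help where the earlier dose was only preventive cover.

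**Whether cover would be that short.** No section describes one-day cover for a major procedure. The window also counts antithrombotic days, and Protocol Table 10 records completion of cover at a visit on surgery day 2 to 14 or on day 28. Planned surgery is an exclusion criterion, so cases should be few. These points reduce the likely number of cases but leave the rule as it is.

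**Whether the difference is deliberate.** Minor procedures may need no supplemental treatment, which would leave a one-day window, so a time minimum is most obviously useful there. That is a plausible reason, but the SAP does not give it, and it applies equally to a major procedure with brief cover.

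**Whether other analyses deal with it.** SAP 6.3.1.2 has a treatment-policy analysis that leaves out events due to surgery, and a sensitivity analysis that keeps all bleeds. They bracket the effect but do not alter the primary analysis. The first may even drop a bleed that the primary analysis counts.

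**Stronger readings that the documents do not support.**

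- A reader might infer that short cover is more likely on fitusiran, because Protocol 6.6 says that for these patients "the perioperative treatment plan should be developed using the same principles as bleed management". Those principles and Table 4 limit the size and spacing of doses; they do not limit the number of days of cover. Section 6.6 also points to antithrombin replacement where those doses are insufficient, which would bring the longer antithrombin exclusion.
- A reader might infer that the spontaneous bleeding rate is affected too. Protocol 7.2 reserves that term for bleeds without an apparent or known reason, so a surgical bleed would enter only if misclassified.
- In the other direction, a reader might treat perioperative cover as prophylaxis, so that the exclusion after prophylactic treatment covers everything. That would make the surgery items largely redundant and is not the natural reading.

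**Conclusion.** The asymmetry is real, and no other provision of the SAP reliably repairs it. As written, the major-surgery exclusion can be shorter than the minor-surgery exclusion, and it is narrower than Protocol 8.2.5.1 without a stated reason.

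The consequence rests on three conditions: cover after a major procedure ends less than 72 hours after surgery; a treated surgical bleed starts after the last cover day but within those 72 hours; and its treatment is not counted as part of the perioperative plan. The documents do not say how often these occur together.

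The size is small: 1.68 on one patient's ABR and about 0.02 on the mean of an 80-patient arm. Five such bleeds, all on fitusiran, would move the planned rate ratio only from 0.222 to 0.230, against fitusiran. It would be wrong to infer a threat to the trial's conclusion or power, or a bias that favours one arm. This is a point of consistency in the specification, worth settling before it can become a dispute over individual bleeds.

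**What to change.** Before database lock, use one rule in SAP 6.3 for both major and minor surgery: the excluded period starts on the day of surgery and ends at the later of (a) the last day of supplemental hemostatic or antithrombotic treatment under the perioperative plan and (b) 72 hours after the end of surgery. Record in the SAP's change history how this differs from Protocol 8.2.5.1 and why. If the sponsor prefers to keep different rules, the SAP should state the reason.

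The change concerns the analysis window only. It leaves the protocol's perioperative period, which also governs study dosing, as it is, and needs no new data. For bleeds that start within 72 hours of surgery, it also removes the question of whether their treatment belongs to the perioperative plan.

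The cost is a few words and, where cover ends on the day of surgery, 3 more excluded days for that procedure (217 − 214), or 3/218 = 1.4% of that patient's efficacy period. Sample size and power are essentially unchanged.
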